8.1.6 Follow up visits (visit 14 and 15)

FU1 should be scheduled 7 days (+ 3 days) after last dose of trial product and FU2 should be scheduled 30 days (+ 3 days) after last dose of trial product. At FU1 information on antidiabetic treatment, any AEs and hypoglycaemic episodes occurring since visit 13 must be collected and recorded in the eCRF. At FU2 information on antidiabetic treatment and any MACE occurring since visit 13 must be collected and recorded in the eCRF.

8.1.7 Unscheduled visits

Unscheduled visits can be performed at any time at the discretion of the investigator. An unscheduled visit must be performed if:

- An AE occurs that needs further attention
- Additional laboratory samples are needed due to an AE requiring special forms in the eCRF (see section [12.2](#))
- A confirmatory pregnancy test is needed
- A blood re-sampling related to a specific visit (if not possible to schedule the re-sampling within the visit window). Only if initial blood sample for some reason was not able to be analysed
- Confirmatory FPG test for rescue criteria evaluation

For the above an unscheduled visit form must be completed in the eCRF, indicating the reason for the visit.

An unscheduled visit form should not be completed if the subject attends the trial site for a blood re-sampling within the visit window. Instead a requisition form must be completed with the visit number the re-sampling refers to and the data must be entered to the eCRF for the corresponding visit. Also, additional trial product dispensing or auxiliary supply dispensing does not require the use of the unscheduled visit form. An additional dispensing session should be made in the IWRS prior to additional trial product dispensing.

8.1.8 Premature discontinuation of trial product

Subjects discontinuing trial product prematurely due to any of the criteria for premature discontinuation of trial product (see section [6.4](#)) will be called in for an EOT visit corresponding to visit 13 as soon as possible after discontinuation of trial product (i.e., day of last dose of trial product). Subject will be asked to bring the current diary and all dispensed trial product. FU1 and FU2 should be performed as described in section [8.1.6](#).

Once FU1 and FU2 are completed a phone contact should be performed every 3rd month. Information of antidiabetic treatment and any SAEs occurring since last contact must be collected and recorded in the eCRF. Phone contact must be documented in the medical record and eCRF. The subject must finally come in for a visit 13A at week 104 to report antidiabetic medication, SAEs and have a blood sample taken to measure HbA_{1c}.

Final drug accountability must be done once the subject has discontinued the trial product and the premature discontinuation must be recorded in the IWRS through a treatment discontinuation session.

The reason for the premature discontinuation of trial product must be recorded in the eCRF.

8.1.9 Withdrawal of consent

If a subject decides to withdraw from the trial, the investigator should aim to undertake procedures similar to those for visit 13, FU1 and FU2 (see section [8.1.6](#)) as soon as possible after the last dose of trial product.

The end-of-trial form must be completed, and final drug accountability must be performed even if the subject is not able to come to the trial site. A treatment discontinuation session must be made in the IWRS. The case book must be signed.

Although a subject is not obliged to give his/her reason(s) for withdrawing from a trial, the investigator must make a reasonable effort to ascertain the reason(s), while fully respecting the subject's rights. Where the reasons are obtained, the primary reason for not completing the trial must be specified on the end-of-trial form in the eCRF.

8.2 Subject related information

Demography

Demography consists of:

- Date of birth (according to local regulations)
- Sex
- Race (according to local regulations)
- Ethnicity (according to local regulations)

8.2.1 Concomitant illness and medical history

A **concomitant illness** is any illness that is present at the start of the trial (i.e. at visit 1) or found as a result of a screening procedure. Concomitant illness includes any pre-planned procedures, surgery and any intermittent illness (e.g. allergies) that may not be apparent at the time of screening. T2DM should not be recorded as concomitant illness. Any change to a concomitant illness should be

recorded during the trial. A clinically significant worsening of a concomitant illness must be reported as an AE.

Medical history is a medical event that the subject has experienced in the past. The information collected for concomitant illness and medical history should include diagnosis, date of onset and date of resolution or continuation, as applicable.

Diagnosis of diabetes is an account in the eCRF of the date of diagnosis of diabetes.

Diabetes treatment history/diabetes complication is an account in the eCRF where information about current diabetes treatment, dose of current diabetes treatment, start date of current diabetes treatment is collected. It is also an account in the eCRF of medical events and complications related to diabetes i.e. diabetic retinopathy/neuropathy/nephropathy and macro angiopathy (including peripheral vascular disease). Details of all relevant diabetes complications must be recorded at trial entry (i.e. at screening visit). The information collected for diabetes complications should include diagnosis and date of onset.

Family history of diabetes is an account in the eCRF where information about the family history of diabetes is collected.

8.2.2 Concomitant medication

A **concomitant medication** is any medication, other than IDegLira or IGlar which is taken during the trial, including the screening and follow-up periods.

Details of any concomitant medication must be recorded at visit 1. Changes in concomitant medication must be recorded at each visit as they occur.

The information collected for each concomitant medication includes trade name or generic name, indication, start date and stop date or continuation.

If a change is due to an AE, then this must be reported according to section [12](#). If the change influences the subject's eligibility to continue in the trial, the monitor must be informed. Please see section [6.4](#).

8.2.3 Smoking status (Tobacco use)

Details of smoking status must be recorded at visit 1. Smoking is defined as smoking at least one cigarette, cigar or pipe daily. The collected information should include whether or not the subject smokes or has smoked. If the subject smokes or has smoked, record approximately when the subject started smoking and, if applicable, when the subject stopped smoking.

8.3 Assessments for efficacy

Body measurements

Height

Height is measured without shoes in centimetres (cm) or inches (inch) and rounded to the nearest cm or inch.

Body weight

Body weight should be measured without shoes and only wearing light clothing in kilograms (kg) or pounds (lb) with one decimal. The measurements are to be performed in a fasting state, except for the measurement at visit 1. Body weight should be assessed with the same equipment throughout the trial, if possible.

Body Mass Index (BMI)

BMI will be automatically calculated in the eCRF once height and weight are entered.

8.3.1 Self-measured plasma glucose

At visit 1 the subjects will be provided with a BG meter including lancets, plasma-calibrated test strips and control solutions as well as instructions for use. The subjects will be instructed in how to use the device and the instruction will be repeated as necessary during the trial.

The BG meters use test strips calibrated to plasma values. Therefore, all measurements performed with capillary blood are automatically calibrated to plasma equivalent glucose values, which will be shown on the display of the BG meter.

Subjects should be instructed in how to record the results of the SMPG values in the diaries.

Quaque die

Subjects should perform QD SMPG measurements in a fasting state. For definition of fasting state see section [8.1](#). Diabetes medication (including trial products) should be withheld until after the measurement.

9-point profile

Subjects should perform SMPG measurements and record the obtained values for a 9-point profile within a week prior to visit 2, 7 and 13 on a day where the subject does not anticipate unusual strenuous exercise.

The SMPG values obtained from the measurements should be recorded in the diary (including clock time and date for the measurement) at the following time points, always starting with the pre-breakfast measurement:

- Before breakfast (this will be the SMPG of that day)
- 90 min after the start of the breakfast
- Before lunch

- 90 min after the start of lunch
- Before dinner
- 90 min after the start of dinner
- At bedtime
- At 4 am
- Before breakfast the following day (this will be the SMPG of that day)

8.4 Assessments for safety

Adverse events (AEs)

All AEs must be collected and reported according to the procedures described in section [12.](#)

Adverse Events requiring special forms in the eCRF

For some AEs the investigator must fill in special forms in the eCRF. The AEs that require special forms in the eCRF are:

- Cardiovascular events
- Pancreatitis
- Neoplasms
- Thyroid disease

In case any of these events fulfil the criteria for a SAE, please report accordingly. See section [12.2.](#)

Cardiovascular events

Cardiovascular events that are suspected as being related to one of the three categories below should be reported on the designated form in the eCRF:

1. Acute coronary syndrome

All types of myocardial infarction (MI) or hospitalisation for unstable angina, for further information (see [Appendix A](#)). If an event of acute coronary syndrome is observed during the trial, this must be recorded as an AE and on a specific acute coronary syndrome form in the eCRF. The following information must be reported if available:

- Duration of symptoms
- Changes in ECG
- Collection of cardiac biomarkers
- Cardiac imaging
- Cardiac stress testing
- Angiography
- Use of thrombolytic drugs
- Coronary revascularisation

2. Cerebrovascular events, e.g., stroke or transient ischemic attack (TIA)

If a cerebrovascular event is observed during the trial, this must be recorded as an AE and on a specific cerebrovascular event form in the eCRF. The following information must be reported if available:

- Type of event (e.g., stroke or TIA)
- Contributing condition
- Neurologic signs and symptoms
- History of neurologic disease
- Imaging supporting the condition
- Treatment given for the condition

3. Heart failure

If an event of heart failure requiring hospitalisation (admission to an in-patient unit or a visit to an emergency department that results in at least a 24 hour stay) is observed during the trial, this must be recorded as an SAE and in addition on a specific cardiovascular event form in the eCRF.

The following information must be reported if available:

- Signs and symptoms of heart failure
- NYHA Class
- Supportive imaging
- Supportive laboratory measurements
- Initiation or intensification of treatment for this condition

Pancreatitis

If a subject is diagnosed with pancreatitis during the trial, this must be recorded as an AE and on a specific pancreatitis event form in the eCRF. The following information must be reported if available:

- Signs and symptoms of pancreatitis
- Specific laboratory test supporting a diagnosis of pancreatitis:
 - Amylase
 - Lipase
 - ALAT and ASAT
 - Bilirubins, total
 - Alkaline Phosphatase
- Imaging performed and consistency with pancreatic disease.
- Complications to the event
- Relevant risk factors for pancreatic disease including:
 - History of gall-stones
 - History of pancreatitis
 - Family history of pancreatitis
 - Trauma

Neoplasm

All events of neoplasm (excluding thyroid neoplasm, but including malignant neoplasm, in situ neoplasm and benign neoplasm) must be recorded as an AE and on a specific neoplasm event form in the eCRF. The following information must be reported if available:

- Type of neoplasm
- Symptoms leading to identification of event
- Diagnostic imaging
- Pathological examination results
- Treatment for the event
- Participation in screening programs
- Risk factors associated to the event

Thyroid disease

Subjects scheduled for thyroidectomy (partial or total) for any reason during the trial, must be instructed to inform the investigator prior to their operation. If an event of thyroid disease, including any thyroid neoplasms observed during the trial, this must be recorded as an AE and on a specific thyroid disease event form in the eCRF. The following information must be reported if available:

- History of thyroid disease
- Signs and symptoms leading to investigations of thyroid disease
- Specific laboratory tests describing thyroid function including:
 - Thyroid stimulating hormone (TSH)
 - Total and free triiodothyronine (T3) and thyroxine (T4) and Free Thyroid Index
 - Calcitonin
 - Thyroid Peroxidase antibodies
 - Thyroglobulin and Thyroglobulin antibody
 - TSH receptor antibody
- Diagnostic imaging performed and any prior imaging supporting the disease history
- Pathologic examinations
- Treatment given for the condition
- Risk factors identified
- Family history of thyroid disease

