6.4 Premature discontinuation of trial product

All efforts should be made to keep the subjects on trial product. In case a subject stops taking the trial product the subject should be encouraged to re-commence the treatment.

The trial product must be discontinued if the subject meets rescue criteria or if following applies:

- Investigator suspect acute pancreatitis. All drugs suspected to relate to this condition must be discontinued until confirmatory tests have been conducted and appropriate treatment should be initiated

The trial product must be permanently discontinued if the following applies:

- Included in the trial in violation of the inclusion and/or exclusion criteria
- HbA_{1c} is $\geq 7\%$ measured at 2 consecutive visits from week 26 (including week 26 if HbA_{1c} was $\geq 7\%$ at week 12)
- Pregnancy
- Intention of becoming pregnant
- Participation in another clinical trial throughout the trial
- In case the calcitonin value is ≥ 50 ng/L. Please see [Appendix B](#)
- Initiation or significant change in concomitant medications (in excess of 14 days) which in the investigator's opinion could affect weight or glucose metabolism
- Subjects that are diagnosed with acute pancreatitis (as a minimum 2 of 3: characteristic abdominal pain, amylase and/or lipase $> 3\times$ upper normal range or characteristic findings on ultrasound, computerised axial tomography/magnetic resonance imaging)

Permanent premature discontinuation of treatment with trial product will not lead to subject withdrawal from the trial. Trial product may be permanently discontinued at the investigator's discretion in case of a safety concern, unacceptable intolerance, or if a subject is judged to be non-compliant with trial procedures.

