12.2 Reporting of adverse events

All events meeting the definition of an AE must be collected and reported. This includes events from the first trial-related activity after the subject has signed the informed consent until the end of the post-treatment follow-up period. At FU1 all AEs must be collected. At FU2 potential MACE occurring in the period between visit 13 and FU2 must be collected.

Subjects discontinuing trial product prematurely (see section [6.4](#)) will be contacted every 3rd month and asked for information about antidiabetic medication and serious adverse events (SAEs). These subjects should finally come in for a visit 13A at week 104, only to assess antidiabetic medication, SAEs and a blood sample to measure HbA_{1c}.

The events must be recorded in the applicable eCRF forms in a timely manner, see timelines below and [Figure 12-1](#).

During each contact with the trial site staff, the subject must be asked about AEs and technical complaints, for example by asking: "Have you experienced any problems since the last contact?"

All AEs, observed by the investigator or subject, must be reported by the investigator and evaluated. Novo Nordisk assessment of expectedness is performed according to the following reference documents:

- IDegLira: Current version of the Company Core Data Sheet or any updates hereof.
- IGlar: European Summary of Product Characteristics current version or any updates hereof.⁵

All AEs must be recorded by the investigator on an AE form. The investigator should report the diagnosis, if available. If no diagnosis is available, the investigator should record each sign and symptom as individual AEs using separate AE forms.

For SAEs, a SIF must be completed in addition to the AE form. If several symptoms or diagnoses occur as part of the same clinical picture, one SIF can be used to describe all the SAEs.

For AEs requiring additional information, a specific event form in addition to the AE form must be completed.

MESIs (medication errors), regardless of seriousness, must be reported using both the AE form and the SIF and a MESI form. The MESI form is a form tailored to collect specific information related to the individual MESI.

For AEs requiring adjudication, the event specific adjudication form must be completed.

The AE form for a non-serious AE not fulfilling the MESI or additional data collection criteria should be signed when the event is resolved or at the end of the trial.

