12.7.2 Event adjudication committee

An independent external EAC is established to perform qualitative validation of selected AEs according to pre-defined diagnostic criteria. The validation is based on review of pre-defined clinical data related to the specific AE. The events are reviewed by the EAC in a blinded manner.

The following AEs will be adjudicated in this trial:

- Fatal events
- Cardiovascular events:
 - Acute coronary syndrome
 - Cerebrovascular event
 - Heart failure requiring hospital admission
- Pancreatitis
- Neoplasms (all kinds of abnormal growth) excluding thyroid neoplasm
- Thyroid disease (thyroid neoplasm and/or thyroid disease requiring thyroidectomy)

Event adjudication will be performed for AEs in randomised subjects including AEs with an onset date during the screening period. Event adjudication will not be performed for AEs in screening failures.

The EAC is composed of permanent members who cover required medical specialities. The EAC members must disclose any potential conflicts of interest and must be independent of Novo Nordisk. The role of the EAC is solely to adjudicate events in a blinded manner. The EACs will have no authorisations to impact on trial conduct, trial protocol or amendments.

The EAC will review translated copies in English of medical documentation received in the adjudication packages (for example X-ray, ECGs, ultrasound images, discharge summaries, pathology reports, and death certificates). The EAC can evaluate an event, not initially reported as an AE for adjudication, to be adjudicated. The investigator must provide medical documentation as soon as possible, once the request from Novo Nordisk or the Event Adjudication vendor is received.

AEs for adjudication must be reported according to section [12.2](#). In addition the specific adjudication form should be completed **within 14 calendar days** of the investigator's first knowledge of the AE, and all relevant predefined documents provided according to instructions in the event adjudication site manual.

13 Case report forms

Novo Nordisk will provide a system for the eCRF. This system and support services to the system will be provided by an external supplier.

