Cerebrovascular event (stroke or transient ischemic attack)	
Stroke (ischemic, haemorrhagic or undetermined) is defined as an acute episode of neurological dysfunction, caused by focal or global brain, spinal cord, or retinal vascular injury.
 
Transient Ischemic Attack (TIA) is defined as a transient (<24 hours) episode of neurological dysfunction caused by focal brain, spinal cord, or retinal ischemia, without acute infarction.
	
An FDA guidance document¹ requests that Sponsors demonstrate the cardiovascular safety profile of any new therapy for type 2 diabetes in order to ensure, that the new therapy does not increase the cardiovascular risk to an unacceptable extent.
	All events will be adjudicated

Events with additional data collection and/or events requiring adjudication	Definitions	Rationale	Event Adjudication Committee
Heart failure requiring hospital admission	Clinical manifestations of a new episode or worsening of existing heart failure.	An FDA guidance document ¹ requests that Sponsors demonstrate the cardiovascular safety profile of any new therapy for type 2 diabetes in order to ensure, that the new therapy does not increase the cardiovascular risk to an unacceptable extent.	All cases of heart failure requiring hospitalisation, defined as an admission to an inpatient unit or a visit to an emergency department that results in at least a 24 hour stay, will be adjudicated
Pancreatitis	
Two of the following three diagnostic criteria fulfilling the diagnosis of acute pancreatitis:
 
• Severe acute upper abdominal pain• Elevated blood levels of pancreatic enzymes (lipase, amylase) > 3xUNR• Characteristic imaging finding (ultrasound, computerised axial tomography (CT), magnetic resonance imaging (MRI)) 
Chronic pancreatitis will be defined by characteristic imaging finding (ultrasound, CT, MRI) with abnormal pancreatic function tests or characteristic histological findings.
	Treatment with GLP-1 agonists has been associated with acute pancreatitis. Pancreatitis (including necrotising pancreatitis) is an identified risk according to the Company Core Data Sheet (CCDS) for liraglutide, a component of IDegLira. Novo Nordisk therefore monitors these events closely.	All events will be adjudicated

Events with additional data collection and/or events requiring adjudication	Definitions	Rationale	Event Adjudication Committee

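### Section 8.4 and Appendix A make the open-label investigator's diagnosis the only mandatory way for pancreatitis to reach its event form and blinded adjudication; suspected cases have no stated route except the committee's discretion

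*Protocol*

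**What the plan says.** Five parts of the protocol bear on how a case of pancreatitis is captured.

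- **Event form (section 8.4).** The trigger is a diagnosis: "If a subject is diagnosed with pancreatitis during the trial, this must be recorded as an AE and on a specific pancreatitis event form". For cardiovascular events, the lead sentence of the same section uses suspicion: "Cardiovascular events that are suspected as being related to one of the three categories below should be reported on the designated form".
- **Event definition (Appendix A).** The acute event is defined by "Two of the following three diagnostic criteria fulfilling the diagnosis of acute pancreatitis": pain, pancreatic enzymes above three times the upper normal range, and imaging. All such events are to be adjudicated.
- **Trial product (section 6.4).** Two states are kept apart. One bullet begins "Investigator suspect acute pancreatitis" and calls for action on trial product while confirmatory tests are done. A later bullet covers subjects diagnosed with at least two of three criteria. Amendment 3 edits the first bullet but keeps the suspicion trigger.
- **Adverse event recording (section 12.2).** "If no diagnosis is available, the investigator should record each sign and symptom as individual AEs using separate AE forms". For the adjudication form: "For AEs requiring adjudication, the event specific adjudication form must be completed".
- **Adjudication (section 12.7.2).** Pancreatitis is on the list, and "The events are reviewed by the EAC in a blinded manner". The EAC may also take up an event that was not initially reported for adjudication, and investigators must supply documents when the sponsor or the adjudication vendor asks.

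No amendment shown changes the pancreatitis trigger in 8.4.

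**The concern.** Blinded adjudication in an open-label trial is meant to keep knowledge of treatment out of the decision on whether an event counts. That works only as far as the entry point is wide. Here the mandatory entry point is already a diagnosis, made at the site by someone who knows the arm.

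The arm could matter. Section 18.1 classes pancreatitis as an identified risk of GLP-1 receptor agonists, so of IDegLira and not of IGlar. It also describes gastrointestinal events as a class effect, and abdominal pain with vomiting as the usual presentation of pancreatitis. An investigator who knows the treatment could be readier to diagnose (known risk) or readier to dismiss (expected gastrointestinal effect). The protocol gives no ground for saying which would prevail.

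At stake is the completeness of the pancreatitis count in each arm, and whether the count after adjudication is as free of unblinded judgement as a reader would suppose.

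**Working it through.** The protocol gives no expected pancreatitis rate and no figure to reproduce. The check is mainly a comparison of text.

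**1. Is diagnosed just loose wording in 8.4?** No. Section 6.4 uses the same word and attaches a minimum of two of three criteria to it. Appendix A uses a near-identical test; the pain item differs (characteristic abdominal pain in 6.4, severe acute upper abdominal pain in Appendix A). Section 6.4 also treats suspicion as a distinct earlier state.

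**2. What happens to a case that is suspected and then rejected by the investigator?**

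| Step | Section | Result |
|---|---|---|
| Suspicion arises | 6.4 | Action on trial product, confirmatory tests |
| Investigator decides it is not pancreatitis | 8.4 | No pancreatitis form required |
| Recording without a diagnosis | 12.2 | Separate sign and symptom AEs |
| Adjudication form | 12.2, 12.7.2 | Required only for listed events; abdominal pain is not listed |
| EAC takes it up anyway | 12.7.2 | Possible, at discretion |

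**3. Does anything make the last step systematic?** Amylase and lipase are measured in both arms, but the protocol links no value to the form or to adjudication. It states no search of symptom AEs. The event adjudication site manual mentioned in 12.7.2 is not shown and may hold such a rule.

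**4. What the filters do.** Among true cases in an arm, let *s* be the share suspected, *d* the share of those that the investigator diagnoses, and *r* the share of the undiagnosed that the EAC recovers under 12.7.2. With equal numbers of true cases, the count reaching the EAC is proportional to:

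- current text: *s* × [*d* + (1 − *d*) × *r*]
- suspicion trigger: *s*

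Illustration, all inputs assumed, with *s* equal in both arms and *r* = 0:

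- *d* = 80% on IDegLira, 60% on IGlar: ratio 0.8/0.6 = 1.33
- *d* = 80% and 70%: 0.8/0.7 = 1.14
- arms exchanged: 0.6/0.8 = 0.75 and 0.7/0.8 = 0.88

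With *r* = 1 in both arms every ratio is 1.0; a common *r* in between gives values in between. Under the suspicion trigger the ratio is 1.0 if *s* is equal, and otherwise equals the ratio of the two values of *s*.

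These figures show how the filter works. They do not estimate its effect in this trial.

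**5. Workload.** If 1–2% of 1000 subjects had a suspected event (assumed): 0.01 × 1000 = 10 and 0.02 × 1000 = 20 packages in all.

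**The case against.** The strongest reply is that a reader might infer that pancreatitis reaches the EAC only after the investigator has diagnosed it, so that adjudication can remove cases but not add them. The protocol does not support that. Section 12.7.2 lets the EAC take up events not initially reported for adjudication, and documents come on request, so a missing form does not close the route. Section 12.7.2 also lists pancreatitis without restricting it to diagnosed cases. Rejected cases leave traces: symptom AEs, enzyme results, and the recorded reason where trial product is discontinued prematurely. All of this stands. What remains is that the route is discretionary and the protocol does not say what should set it off.

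The contrast with cardiovascular events is also less clean than it first looks. Suspicion appears only in the lead sentence; the item text reads, for example, "If an event of acute coronary syndrome is observed during the trial", and heart failure counts only with hospitalisation. This stands too, but the point does not need the contrast. The mismatch between 6.4, which recognises suspected pancreatitis, and 8.4, which does not, is enough.

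Third, suspicion is more subjective than a two-of-three rule, and section 18.1 states the response to suspicion for IDegLira by name. A suspicion trigger could therefore carry its own arm difference. That is correct, and if the two filters pulled in opposite directions, removing one could move the ratio away from 1. But diagnosed cases are a subset of suspected ones. The wider trigger cannot lose a true case that the present one catches, and it hands the criteria to the blinded committee.

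Finally, section 17.4.1.2 plans only descriptive summaries of treatment-emergent adverse events and names no between-arm analysis of EAC-confirmed pancreatitis. No planned test or estimate is shown to be biased.

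**Conclusion.** The point holds as a gap in ascertainment. The only mandatory route onto the pancreatitis form, and so to blinded adjudication, is a diagnosis by the open-label investigator on essentially the EAC's own criteria. Suspected cases, which 6.4 recognises, depend on a discretionary pick-up with no trigger stated in the protocol. Unblinded judgement can therefore influence the count for an identified risk of one arm, upwards or downwards.

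Its size is unknown. A reader might take a ratio such as 1.33 as the likely distortion, but it follows from assumed diagnosis rates with no source in the protocol, and the same assumptions with the arms exchanged give 0.75. With so few events, such a ratio could not be told apart from chance.

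This is a low-priority improvement. It rests on the protocol as shown; a search rule or enzyme trigger in the site manual would narrow it further.

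**What to change.** In sections 8.4 and 12.7.2 and in Appendix A, make suspected or diagnosed pancreatitis the trigger for the event form and for adjudication. Every case suspected under 6.4 then gets the form and goes to the EAC, which applies the two-of-three criteria. In Appendix A, keep those criteria as the EAC's confirmation standard and not as the condition for reporting. Leave the trial-product rules in 6.4 unchanged.

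The cost is wording in three places and a small number of extra packages to an existing committee, most of which it would reject (10–20 suspected-event packages in all, on the assumption above). The change removes one unblinded filter. It does not remove a difference between arms in how readily pancreatitis is suspected, and the trial report should say so.
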